Between Visits 3 and 4 participants will receive a daily online REDCap survey (named E-cigarette and Cigarette Use Log (Online Survey Version) under Participant Entered Measures) via a text message to their cell phone with a link to the survey using the Twilio services. The survey will ask about the number of e-cig uses, number of cigarettes smoked, and any non-study cigarettes smoked. During the first week of the online survey, participants will also be asked about nicotine withdrawal symptoms. If participants do not have a reliable cell phone and internet access they will complete the information on paper logs.

Procedures during COVID-19:

Visit 3 will be completed in-person. Participants will be screened for COVID-related symptoms using a modified version of the Patient Screening Questions from the Penn State Health website. Questionnaires for Visit 3 outlined in Revised Table 1 will be sent to the participant via a survey link before the in-person visit. Participants will be encouraged to complete the questionnaires 2 hours before the visit, but will have up to 24 hours to complete them after the visit. Participants will be asked for their cigarette log from the prior week. Biomeasures will be obtained (e.g., pulmonary function tests, weight, exhaled CO, blood pressure, pulse) as outlined in Revised Table 1. Urine samples will be collected at this visit. A pregnancy test will be given to women of childbearing potential.

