Participants who complete the Baseline Phase and are eligible to continue in the study will enter the Randomized Phase. They will be randomized to either continue to smoke the same NNC SPECTRUM (11.6 mg nicotine) research cigarettes they smoked in the Baseline Phase or switch to VLNC SPECTRUM research cigarettes (0.2 mg nicotine) AND also be randomized to either a nicotine-containing (5% nicotine liquid) or placebo (0% nicotine liquid) JUUL e-cig (JUUL Labs, Inc.). Participants will receive a 4-week supply of research cigarettes (130% of baseline daily consumption) and e-liquid pods to last 28 days until the next appointment. They will be shown how to use the e-cig and how to charge it. Participants may be shown videos from the JUUL website (<https://www.juul.com/learn/device>) for more information on how to use and charge the device called, 'How to use JUUL' and 'How to set up your JUUL Device'. We will also give them a handout called JUUL E-Cigarette Instructions. Within the JUUL device packaging there is a paper insert with instructions and information. This insert will be given to the participant when we give them the JUUL device. The study staff will give participants e-cig and cigarette use logs and instruct them to record daily use. Participants will be encouraged/provided advice to substitute some of their cigarettes with their e-cigarette.

All participants will be asked about their use of other nicotine/tobacco products and if they vaped/smoked any other substances other than nicotine/tobacco as this could affect the urine biomarkers collected during the study (e.g. carbon monoxide and cotinine levels). Participants will also be reminded to only use research cigarettes and not commercial brand cigarettes, as well as only using the e-liquid pods received by researchers. Participants will be compensated for completing the study visit and procedures.

Between Visits 3 and 4, participants will receive a daily online REDCap survey (named E-cigarette and Cigarette Use Log (Online Survey Version) under Participant Entered Measures) via a text message to their cell phone with a link to the survey using the Twilio services. The survey will

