7.4.2 Treatment Regimen

At Visit 2, all participants will be given Normal Nicotine Cigarettes (11.6 mg nicotine/cigarette) to use for 2 weeks. At Visit 3, participants will be randomized into one of the 4 arms described below:

	5% Nicotine E-cig	0% Nicotine E-cig
Normal Nicotine Cigarettes (NNCs) (11.6 mg nicotine/cigarette)	Arm 1	Arm 2
Very Low Nicotine Cigarettes (VLNCs) (0.2 mg nicotine/cigarette)	Arm 3	Arm 4

Participants will be provided with these products starting at Visit 3 (Week 0) and continue to use these products ad libitum through Visit 7 (Week 16).

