8.3 Statistical methods

Basic baseline statistics including means (standard deviations) and frequency distributions (percentages) will be reported for demographic characteristics, smoking characteristics, nicotine dependence, and nicotine and toxicant exposure. Characteristics will be reported by the four treatment arms to identify treatment arm imbalances. Numerical baseline characteristics will be compared among four arms using ANOVA tests or nonparametric Kruskal-Wallis tests when appropriate. Categorical variables will be compared using chi-square tests or Fisher's exact tests. The focus of the statistical analysis will be the difference between four trial arms in terms of the biomarkers of toxicity and health effects. Analyses will be conducted in two approaches, which will address our research questions in two different angles. The first approach is a simplified and streamlined one, the longitudinal measurements of these biomarkers over the 16-week period will be summarized by using just the baseline (visit 3, pre-randomization) and final (visit 7, end of randomization period) measurements. Analysis of Covariance (ANCOVA) models will be used to compare the final measurements among the four arms, while the baseline measurements will be treated as controlled covariates in the model. Specifically, the comparisons between arms 1 and 3 and between arms 2 and 4 answer whether switching to very low nicotine cigarettes leads to lower markers of harm as compared to continuing on normal nicotine cigarettes. This addresses specific Aim 1. Furthermore, we will study if this reduction is the same when combined with 5% nicotine e-cigs (arms 1 and 3) and combined with placebo e-cigs (arms 2 and 4). Similarly, comparison between arm 1 and arm 2 reveals if access to nicotine versus placebo e-cigs impacts these biomarkers. This will address Aim 2. In particular, we will test if the arm 3 has the best outcome as stipulated in Aim 2. These analyses will be conducted using ANCOVA models with interaction terms between traditional cigarettes (normal nicotine vs. very low nicotine) and e-cig (5% vs. 0%). Appropriate transformation may be done on some of the outcome variables (for example log-transformation) to make sure the underlying statistical assumptions are all satisfied. Note that for NNAL, one of our main biomarkers of toxicity; it can only be analyzed using the first approach due to the limitation of number of measures.

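### Under the COVID-19 procedures, Visit 3 questionnaires may be answered after randomisation, although Section 8.3 takes Visit 3 as the pre-randomisation baseline covariate for questionnaire outcomes such as Kessler-6

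*Combined protocol and SAP*

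**What the plan says.** **Questionnaire window.** In the COVID-19 text for Visit 3 (Section 7.2), the visit is in person and its questionnaires go out by link beforehand. Participants are asked to finish two hours ahead, "but will have up to 24 hours to complete them after the visit". The standard Visit 3 text has no such window: measures are completed on a study laptop or with a coordinator.

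**Randomisation and products.** Section 7.4.2 states: "At Visit 3, participants will be randomized into one of the 4 arms described below". Section 7.2 gives the condition for entry: "Participants who complete the Baseline Phase and are eligible to continue in the study will enter the Randomized Phase". It continues: "They will be randomized to either continue to smoke the same NNC SPECTRUM (11.6 mg nicotine) research cigarettes" or switch to very low nicotine content (VLNC) cigarettes, with a second allocation to a nicotine or placebo e-cigarette. Participants leave with both products and with advice to replace some cigarettes by vaping. Section 7.4.2 dates free use of the products from Visit 3.

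**Analysis.** In the ANCOVA approach of Section 8.3, the biomarker measurements are to be "summarized by using just the baseline (visit 3, pre-randomization) and final (visit 7, end of randomization period) measurements", with the baseline value as covariate. The mixed models also adjust for a baseline value taken before randomisation, without naming a visit. A later paragraph of Section 8.3 applies a similar analysis to the tobacco use, addiction and mental health measures.

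**The concern.** An answer that Section 7.2 allows can break the definition in Section 8.3. A participant who submits the Visit 3 questionnaires that evening or the next morning may already have been using the assigned products for hours. The analysis would still treat that score as pre-treatment.

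Adjusting for a covariate that treatment has already moved shifts the treatment contrast. The first day is a plausible time for movement. The trial studies an abrupt switch, Section 2.3 describes this population as vulnerable to withdrawal, and the protocol itself asks about withdrawal symptoms daily in the first week after Visit 3. Kessler-6 is a named secondary endpoint and mental health is part of Aim 1, so an artefact in either direction would bear on a question the trial was set up to answer.

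**Working it through.** The documents contain no figure to reproduce here. The check compares the sections and then works out the size under assumptions.

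**Step 1: can a permitted answer fall after the start of treatment?** Allocation and dispensing take place at Visit 3, and the window closes 24 hours after Visit 3. So it can. No section requires the questionnaires before allocation, and none says how to handle late answers.

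**Step 2: which outcomes are reached?**
- Kessler-6 and the Minnesota withdrawal scale are marked at both Visit 2 and Visit 3 in Revised Table 1, so they are reached.
- The cigarette dependence index, CES-D/QIDS, OASIS and the Perceived Stress Scale cannot be settled. Their marks start one column earlier in the available text of Revised Table 1, and the columns may have shifted.
- The e-cigarette dependence index starts after randomisation and has no baseline.
- NNAL and the other urine markers, exhaled CO and spirometry (when performed) are taken in person at the visit, so they are not reached.

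**Step 3: form of the bias.** Let Δ be the true week-16 difference (VLNC minus normal nicotine, on a scale where higher is worse), b the slope on baseline, f the share of randomised participants who answer after starting products, and d the first-day difference between arms. Then

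ANCOVA estimate ≈ Δ − b × f × d.

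- If d > 0 (more distress on VLNC on the first day), the estimate moves in favour of VLNC. A true harm is understated, and a true benefit is overstated.
- If d < 0, it moves the other way.
- If d = 0, there is no bias.

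**Step 4: size.** All inputs are assumptions: b = 0.5 to 0.7, f = 0.25 to 0.5, d = 0.2 to 0.4 SD.
- Low end: 0.5 × 0.25 × 0.2 = 0.025 SD.
- High end: 0.7 × 0.5 × 0.4 = 0.14 SD.

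These figures suppose that everyone is randomised under the COVID-19 procedures. If half are, f halves and the range becomes 0.0125 to 0.07 SD.

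**Step 5: the same result as a proportion.** Suppose the first-day effect is a fraction k of the week-16 effect, with the same sign. Then the estimate divided by the true effect is 1 − b × f × k.
- f = 0.3, k = 0.25, b = 0.5: 1 − 0.0375 = 0.9625, about 96%.
- f = 0.5, k = 0.5, b = 0.7: 1 − 0.175 = 0.825, or 82.5%.
- k = 0: 100%.

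A simulation with 400,000 participants per setting gave 0.964 and 0.83 for the first two, in agreement with the formula.

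**Step 6: is Visit 2 a safe fallback?** Visit 2 is at week −2 and Visit 3 at week 0, 14 days apart. Visit 2 carries the same 24-hour allowance, so its latest permitted answer falls about 13 days before randomisation.

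**The case against.** The best reply is that Section 8.3 already asks for a value from before randomisation, which a late answer would not be. Section 7.2 admits to the randomised phase only those who have completed the baseline phase, and Revised Table 1 places Visit 3 in that phase. On this view only an operational rule is missing. That is a fair description of the gap, but it does not close it. The 24-hour allowance is written specifically for the visit at which allocation happens, and nothing tells the analyst to reject a score recorded under the Visit 3 label.

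Other parts of the reply stand:
- **Scope.** A reader might infer that every ANCOVA and mixed model is compromised, including the primary analysis. The documents do not support this. The explicit Visit 3 definition is written for biomarkers, which are collected in person; questionnaires enter through the later extension in Section 8.3.
- **Direction.** A reader might infer that the bias must hide an effect. That holds only if the first-day and week-16 effects have the same sign. The protocol hypothesises less distress by week 16, so early withdrawal followed by later improvement would exaggerate the benefit.
- **Concealed harm.** A reader might infer that mental health harm would go unseen. First-week withdrawal is collected separately by daily survey, and adverse events, suicidal ideation and changes in mental health go to the monitoring committee (Section 9.2).
- **Reach.** The COVID-19 procedures are described as temporary, and two of the four arms receive nicotine e-cigarettes, which may soften any first-day difference.

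**Conclusion.** The point holds for questionnaire outcomes of participants who are randomised under the COVID-19 procedures and answer after starting products. Kessler-6 and the Minnesota withdrawal scale are clearly reached; other scales are uncertain. For these answers Section 7.2 permits what Section 8.3 rules out.

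Size and direction are unknown. The 0.025 to 0.14 SD range, the halved range of 0.0125 to 0.07 SD and the 82.5% to 100% retention all rest on assumed slopes, late shares and first-day effects. They show what could happen and do not estimate what did. The text permits late completion but does not show that it occurs. The primary endpoint is untouched. The matter is worth correcting because it concerns a named secondary endpoint and the correction is small.

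**What to change.** **For participants still to be randomised.** Require the Visit 3 questionnaires to be submitted before REDCap releases the allocation, at home beforehand or in clinic if not yet done, and close the link at that point. Visit 3 is in person, and both the questionnaires and the randomisation already run in REDCap.

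**For data already collected.** State in Section 8.3 that:
- survey timestamps will flag Visit 3 answers made after randomisation;
- the Visit 2 score will serve as baseline for those participants where the measure was taken then, as Kessler-6 and the Minnesota withdrawal scale were;
- the number of late answers will be reported by arm;
- a sensitivity analysis will leave out late responders.

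**Cost.** Late responders spend somewhat longer in clinic, at a time when the site wished to limit face-to-face contact. The Visit 2 score belongs to own-brand smoking, before the two weeks on normal nicotine research cigarettes, so it is a somewhat noisier baseline. The sensitivity analysis drops randomised participants for something that happens after allocation, so it should support the main result and not replace it. The analysis needs one timestamp check in the code.

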1.3 Secondary Study Endpoints

Secondary endpoints include exhaled CO, Kessler-6 score, and cigarette/e-cigarette dependence using Penn State Cigarette Dependence Index (PSCDI) and Penn State Electronic Cigarette Dependence Index (PSECDI), at week 16, and cigarette abstinence (no cigarette use in the past 7 days and CO < 6ppm) at week 20.

Additional endpoints include:

Health effects and toxicant exposure measures: Pulmonary Function Tests (PFT), Clinical COPD Questionnaire (CCQ), urinary CYMA (biomarker for acrylonitrile [volatile organic compound] exposure), 3HPMA (biomarker for acrolein [volatile organic compound] exposure, cotinine (biomarker of nicotine exposure)

Mental health measures: Center for Epidemiological Studies-Depression (CES-D), Overall Anxiety Severity and Impairment Scale (OASIS), Quick Inventory or Depressive Symptomatology (QIDS), Perceived Stress Scale (PSS)

Nicotine/Tobacco use and addiction measures: daily cigarette use, daily e-cig use, Fagerstrom Test for Nicotine Dependence (FTND), Hooked on Nicotine Checklist (HONC), , Minnesota Nicotine Withdrawal Scale (MNWS)

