Visits 3-5 and 7 will be completed in-person. Participants will be screened for COVID-related symptoms using a modified version of the Patient Screening Questions from the Penn State Health website. Remote Visit 6 will be completed remotely over Zoom or the telephone. Questionnaires for visits outlined in Revised Table 1 will be sent to the participant via a survey link before the in-person visit. Participants will be encouraged to complete the questionnaires 2 hours before the visit, but will have up to 24 hours to complete them after the visit. Participants will return their e-cig and cigarette use log. Biomeasures will be taken as outlined in Revised Table 1. No biomeasures will be collected at Remote Visit 6. Women of child bearing potential will be retested for pregnancy at Visits 5 and 7.

The study staff will give participants e-cig and cigarette use logs and instruct them to record daily use at each visit. All participants will be asked about their use of other nicotine/tobacco products and if they vaped/smoked any other substances other than nicotine/tobacco at each visit as this could affect the urine biomarkers collected during the study (e.g. carbon monoxide and cotinine levels). Participants will be encouraged/provided advice to substitute some of their cigarettes with their e-cigarette.

Participants will receive a 4-week supply of research cigarettes (130% of daily consumption) and e-liquid pods to last approximately 28 days until the next appointment. At Visit 5, participants will receive an 8-week supply of e-cigarettes and cigarettes due to Remote Visit 6 being a remote visit. Participants will be asked to return all opened, unopened and empty cigarette packs and all used/unused e-liquid pods to the study center at each visit in order to monitor use.

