At Visit 7, participants will return all used and unused research cigarette packs. No more cigarettes will be given. Participants will be allowed to keep their e-cig and unused e-liquid pods until the next visit. Participants will return their e-cig and cigarette use logs. Urine samples for biomarkers will be taken. Participants will complete all biomeasures and questionnaires outlined in Revised Table 1. Participants will be advised to quit smoking completely and provided with the quitline number and sources of free/low cost nicotine replacement therapy (NRT) (see Cigarette Smoking Cessation Tools handout document). The Surgeon General booklet will also be given (see the Consumer Surgeon General Report Booklet document). Participants will be asked about their plans to either (a) go back to their own cigarettes only (b) go back to own cigarettes but supplement with an e-cig, (c) continue using an e-cig only, or (d) quit tobacco/e-cigs completely. Participants will be compensated for completing the study visit and procedures.

A study pulmonologist was added to the study team. We will be monitoring lung function using pulmonary function testing that will be completed at Visits 4, 5, 7. Any significant worsening (10% worsening or greater) in pulmonary function will be documented as an adverse event. These adverse events will be reviewed by the Safety Monitors in a timely manner. In cases where the Safety Monitor suspects that a participant may be having a respiratory adverse event related to the study product, a study pulmonologist will be consulted. The pulmonologist will make any needed medical recommendations and a determination regarding whether the

participant is able to continue with the study. For more urgent and/or serious adverse events, the Safety Monitor and/or the study pulmonologist will be consulted and immediate medical attention will be sought if needed.

Follow-up Visit 8 (Week 20)

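### Under the COVID procedures, week-16 questionnaires may be completed up to 24 hours after Visit 7, once the randomised cigarettes are withdrawn and quitting is advised, yet they are analysed as end-of-randomisation values

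*Combined protocol and SAP*

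**What the plan says.** The COVID text for Visits 4-7 in section 7.2 states that "Visits 3-5 and 7 will be completed in-person". Survey links go out beforehand. On timing, the preferred arrangement is early completion: "Participants will be encouraged to complete the questionnaires 2 hours before the visit". Those who have not done so by then are given a further allowance: "but will have up to 24 hours to complete them after the visit". No exception is made for Visit 7.

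The Visit 7 paragraph of the same COVID text then states:

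- On cigarettes: "At Visit 7, participants will return all used and unused research cigarette packs. No more cigarettes will be given".
- On advice: "Participants will be advised to quit smoking completely and provided with the quitline number".
- On the e-cig: "Participants will be allowed to keep their e-cig and unused e-liquid pods until the next visit".
- On measures: "Participants will complete all biomeasures and questionnaires outlined in Revised Table 1". It gives no order relative to pack return or quit advice.

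Section 1.3 reads "Secondary endpoints include exhaled CO, Kessler-6 score, and cigarette/e-cigarette dependence", with PSCDI and PSECDI as the dependence scales and week 16 as the time point. Section 7.4.2 has participants using the assigned products through Visit 7. Section 8.3 takes the Visit 7 value as the final measurement of the randomisation period. It contains no completion-time rule and no sensitivity analysis for forms entered after the visit.

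The standard (non-COVID) procedure for Visits 4-7 has no 24-hour allowance. Measures are completed on a study laptop or administered by a coordinator.

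**The concern.** A participant who answers within the allowed window, but after leaving Visit 7, no longer has the randomised cigarettes and has just been advised to quit. The answers describe, at least in part, a state that follows the randomised cigarette exposure. The analysis nevertheless labels them week 16.

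The affected outcomes matter to the trial. Aim 1 in section 1.1 names mental health and cigarette addiction at the end of the randomised phase, and Kessler-6, PSCDI and PSECDI are named secondary endpoints.

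The protocol itself gives reasons why a short lag might count. Section 10.0 lists anxiety, restlessness and depressed mood as possible effects of stopping nicotine and says these could affect an existing mental health condition. Section 2.3 cites this population's vulnerability to withdrawal as part of the rationale. The two cigarette groups also lose different products at Visit 7 (11.6 mg versus 0.2 mg nicotine per cigarette), so any shift among late responders could differ by randomised group.

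**Working it through.** The plan has no figure of its own on this point to reproduce. The check is a comparison of the text, followed by an illustration of scale.

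**Text, in order of events at Visit 7 under the COVID procedures**

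1. Questionnaire window: opens before the visit and closes 24 hours after it (section 7.2, COVID text for Visits 4-7).
2. Randomised cigarettes: all packs returned and none issued, at the visit.
3. Quit advice: given at the visit.
4. Randomised e-cig: device and unused pods kept until Visit 8.
5. Analysis label: end of the randomisation period (section 8.3).

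Items 1 to 3 together allow a form to be completed after the cigarette factor has been withdrawn. Item 4 means the e-cig factor has not been withdrawn. Item 5 makes no distinction between early and late forms.

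**Length of the lag**

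The randomised period is 16 × 7 = 112 days. A lag of at most 1 day is 1/112 = 0.9% of it.

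**Illustration of scale**

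Let f be the share of week-16 questionnaires completed after the visit and s the shift in the between-group contrast among those forms, in SD units. Then bias = f × s. The documents give neither f nor s, so both are assumptions.

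| f | s = 0.1 | s = 0.25 | s = 0.5 |
|---|---|---|---|
| 10% | 0.01 | 0.025 | 0.05 |
| 25% | 0.025 | 0.062 | 0.125 |
| 50% | 0.05 | 0.125 | 0.25 |

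For comparison, the cigarette main effect sets arms 1 and 2 against arms 3 and 4, that is 2 × 60 = 120 against 120. The difference detectable with 80% power at two-sided 0.05 is (1.960 + 0.842) × √(2/120) = 0.36 SD.

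**Effect on the error rate if there were no true difference (120 v 120)**

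The noncentrality is bias × √(120/2).

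- f = 25%, s = 0.2: bias 0.05 SD, noncentrality 0.05 × 7.75 = 0.39, rejection probability about 6.7%.
- f = 25%, s = 0.4: bias 0.10 SD, noncentrality 0.10 × 7.75 = 0.77, rejection probability about 12%.

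Both figures are against a nominal 5%. They assume complete data and the same late share and shift across all 240 participants.

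**The case against.** The strongest case on the other side is that this is a small gap.

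- **Limited reach.** It affects only late responders seen under procedures that section 7.2 describes as lasting until in-person research is allowed again. Completion before the visit is encouraged. This stands, and it lowers f.
- **Short lag.** The documents do not give the recall periods of the scales. If an instrument looks back over days or weeks, most of its window is still on product. This stands; a withdrawal or urge scale would plausibly move more than a scale with long recall.
- **Direction unknown.** A reader might infer that very-low-nicotine participants would be relieved by returning to their own cigarettes while normal-nicotine participants would be in withdrawal, so that very-low-nicotine cigarettes would look safer for mental health. The documents do not support this. Both groups receive the same advice and are asked about the same options, including returning to their own cigarettes, and entry required no plan to quit within 3 weeks (section 3.1). Nothing shows that one group quits while the other resumes.
- **E-cig retained.** A reader might also infer that the whole randomised exposure has ended. It has not: device and unused pods stay with the participant until Visit 8, so those assigned 5% pods may still have study nicotine.

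None of this closes the gap. The plan permits a post-withdrawal form, puts no limit on how many there may be, and analyses them as on-product values.

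**Conclusion.** The point holds for the cigarette factor and for questionnaire outcomes only. Under the COVID procedures, week-16 Kessler-6, PSCDI, PSECDI, withdrawal and mood scores from late responders can be recorded after the randomised cigarettes are withdrawn and quit advice is given, while the e-cig remains available. Section 8.3 does not handle this.

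Neither the size nor the direction of any bias can be determined from the documents. The 0.01-0.25 SD range and the 6.7% and 12% error rates rest on assumed late shares and shifts, and show only that the effect could be negligible or could matter.

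It would be wrong to read this as a threat to the primary result. Urinary NNAL is sampled at the visit, as is exhaled CO where it is collected, and neither depends on when a questionnaire is answered.

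The change is worth making because it is cheap and removes an avoidable ambiguity in outcomes that Aim 1 depends on.

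**What to change.** 1. **Timing.** In the COVID text of section 7.2, for Visit 7 only, replace the 24-hour post-visit allowance with completion before the visit, or on site before research cigarettes are collected and quit advice is given. Pack return and the advice themselves need not change.
2. **Forms already completed late.** Keep them in the main intention-to-treat analysis. Setting them to missing would discard outcomes from a possibly non-random subgroup, and section 8.3 states no missing-data method. Flag them by comparing the REDCap completion time with the visit; section 19.1.1 says every interaction with the data is logged.
3. **Analysis.** Add to section 8.3 a sensitivity analysis of the week-16 questionnaire outcomes that excludes flagged forms, and report the number flagged by arm.

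The cost is somewhat longer on-site time at Visit 7 for participants who have not answered beforehand. That runs slightly against the COVID aim of limiting face-to-face contact, but it is avoidable by answering before arrival. No new visit or data item is needed.
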